4.2.2 Protocol deviations

A table of important PDs will be presented overall and by age cohort for the ITT Analysis Set. See [Section 2.2](#) for details, including determination of importance.

Important PDs will be displayed in a data listing by age cohort and patient.

4.2.3 Demographics and baseline characteristics

Demographics data defined in [Section 3.3.1](#) will be summarized for the ITT, MITT and Micro-ITT Analysis Set by age cohort and overall. Baseline length (cm) and weight (kg) will be tabulated.

Relevant surgical and medical history (past and current) including antepartum/ peripartum period will be summarized by MedDRA System Organ Class and preferred term, both by age cohort and overall for the ITT Analysis Set.

The number and percentage of patients with baseline pathogens (Genus and species) by specimen type (blood, CSF, urine, and other specimens) will be summarized by age cohort and overall for the ITT, MITT and Micro-ITT Analysis Set.

Demographics and baseline characteristics, and relevant medical and surgical history data will be listed by age cohort and patient. Baseline culture data including susceptibility (susceptible, intermediate, resistant) and gram stain testing results will be listed by age cohort and patient for the ITT Analysis Set.

4.2.4 Prior and concomitant medications

See [Section 3.3.3](#) for definitions of prior and concomitant medications.

Medications received concomitantly with study therapy, categorized by anatomical therapeutic chemical classification and generic name according to the World Health Organization Drug Dictionary Enhanced (WHODDE, Version 20.0), will be summarized. The number and percentage of patients using at least one medication within each ATC Group and Generic Term will be displayed by age cohort and overall for the Safety Analysis Set. Prior medications will be summarized in an identical fashion. For lactating mothers, maternal prior and concomitant medications will be included in these summaries.

The duration of prior medications defined as the end date – start date +1, will also be summarized for each ATC Group and Generic Term and displayed by age cohort and overall for the ITT Analysis Set. In the event that prior medications had partial dates no imputation will be undertaken and consequently the duration of prior medication will be missing for any such records.

Prior and concomitant medication data will be listed for the ITT Analysis Set by age cohort and patient.

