7.7. Concomitant and other treatments

All prior medications (taken or received within 7 days before the first dose of study therapy) and all concomitant medications (taken during the study), including, but not limited to, all antimicrobials, parenteral nutrition, and blood and blood-component transfusions will be documented. For patients who are being breast fed, all medications taken by the lactating mother for 3 days before first dose of study therapy through SFU will also be recorded.

Concomitant antibacterial therapy is not permitted except in the case of clinical failure.

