3.1.1.1 Adverse events (AE) variables

An AE is the development of any new undesirable medical condition or the deterioration of a pre-existing medical condition following or during exposure to a pharmaceutical product, whether or not considered causally related to the product. An undesirable medical condition can be symptoms (eg, nausea, chest pain), signs (eg, tachycardia, enlarged liver), or the abnormal results of an investigation (eg, laboratory findings). In clinical studies, an AE can include an undesirable medical condition occurring at any time, even if no study therapy has been administered. All AEs will be classified using the Medical Dictionary for Regulatory Activities (MedDRA) version 12.0 or higher.

The term AE is used to include both serious and nonserious AEs. Each AE will be graded for intensity (mild, moderate, severe). If intensity is missing it will be presented as such in the corresponding Tables. Each AE will be assessed for relationship to the study therapy (yes, no) as well. If relationship to study therapy is missing it will be presented as such in the corresponding Tables.

Adverse events will be collected from the time the parent(s)/legal guardian/legally acceptable representative provides informed consent throughout the treatment period up to and including the SFU visit in the study. AEs occurring after the start of administration of the first dose of study therapy or AEs that started prior to treatment and worsened on treatment up to and including the SFU visit will be summarised.

Adverse events of special interest (AESI) will be selected by subsetting MedDRA preferred terms from Pseudomembranous colitis Standard MedDRA Query (SMQ narrow), Anaphylactic reaction (SMQ narrow), Angioedema (SMQ narrow), and Malignancies (SMQ

narrow). The MedDRA preferred terms identifying the AESI were provided by Pfizer, see [Appendix C](#).

Serious adverse events variables

A SAE is an AE occurring during any study phase (ie, treatment, follow-up), that fulfils one or more of the following criteria:

- Results in death
- Is immediately life threatening
- Requires inpatient hospitalization or prolongation of existing hospitalization
- Results in persistent or significant disability or incapacity
- Is a congenital abnormality or birth defect
- Is an important medical event that may jeopardize the patient or may require medical intervention to prevent one of the outcomes listed above

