3.3.2 Definition of prior and concomitant medication

Any medications (non-antimicrobial, antimicrobial, parenteral nutrition and blood/blood-component transfusions) taken by the patient between 7 days prior to study entry (or taken by the lactating mother of breast fed patients within 3 days prior to study entry) and prior to the first dose date of study therapy received will be considered prior medication. Any medication taken by the patient (or by the lactating mother of breast fed patients) at any time between dates of the first dose (including the date of the first dose) of study therapy through the TOC visit, inclusive, will be considered concomitant medication. Any medication started prior to the study entry and ended/ongoing up to the TOC will be considered as both prior and concomitant medication.

If any medications reported are not able to be determined as prior medications or concomitant medications due to missing or partial start dates and/or stop dates, the following imputation rules will be implemented:

- If the year is present but the month and day are missing, then 01JAN will be imputed for the start date and 31DEC for the stop date.
- If the year and month are present but the day is missing, then 01 will be imputed for the start date and the last day of the month for the stop date.

If both stop/start years are missing or both stop/start dates otherwise cannot be imputed, then the date will be treated as missing and the medication will be treated as both prior and concomitant medications.

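### Infant medication tables include the mother's drugs and omit infant drugs first started after TOC, so they can misstate infant use

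*SAP*

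**What the plan says.** SAP 4.2.4 sets the counting unit of the prior and concomitant medication tables: "The number and percentage of patients using at least one medication within each ATC Group and Generic Term will be displayed". This is done for each cohort and for all patients together, in the Safety Analysis Set. Where the mother is breast-feeding, the section adds that "maternal prior and concomitant medications will be included in these summaries". No separate table, column or flag for maternal records is described. The section also plans a summary of the duration of prior medications in the ITT set, and a listing by patient.

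SAP 3.3.2 defines both terms to cover drugs taken by the infant or by the lactating mother of a breast-fed infant. It names antimicrobials and transfusions among the medication types. For the upper time limit, a drug taken from the first dose "through the TOC visit, inclusive, will be considered concomitant medication".

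Protocol 7.7 treats concomitant medications as those taken during the study, with no limit at TOC. Maternal drugs "for 3 days before first dose of study therapy through SFU will also be recorded". Protocol 4.3.2.1 and 4.3.2.2 have concomitant medications recorded at SFU, whether by telephone or in person. In SAP 3.1.1.1, treatment-emergent events "up to and including the SFU visit will be summarised", and SAP 4.2.6.1 uses the same end point.

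**The concern.** There are two separate mismatches.

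The first is who is counted. The denominator is infants, but a drug taken only by the mother can put her infant in the numerator. Antibacterials matter most. Protocol 7.7 does not permit concomitant antibacterial therapy except in clinical failure, so readers will look to this table for other antibacterial treatment alongside the study drug. A maternal antibiotic could not be told apart there from one given to the infant. Because the definition of prior medication also includes the mother, the same problem reaches the prior-medication duration summary. A long-standing maternal drug could contribute a duration longer than the life of an infant enrolled at 7 to under 60 days of age.

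The second is the period covered. A drug or transfusion that the infant first receives after TOC is neither prior nor concomitant under SAP 3.3.2. The protocol collects it, and the event that prompted it is summarised. Relevant events are foreseeable in that interval: Protocol 4.3.2 provides for symptoms of relapse at SFU, and Protocol 1.3 asks that drug-induced haemolytic anaemia be considered if anaemia develops during or after treatment.

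The study is descriptive with safety as its primary objective, so the tables are the result. In cohorts of 8, a single misattributed infant is visible.

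**Working it through.** **Inputs from the documents.** Therapy lasts 2 to 14 days, TOC is 8 to 15 days after the last dose, and SFU is 28 to 35 days after the last dose (SAP 1.2). The plan is at least 24 patients in three cohorts of 8 (SAP 1.2 and 1.3). The documents give no rates of breast-feeding, maternal drug use, infant drug use or transfusion.

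**The plan's own figures.** Maximum participation: 14 + 35 = 49 days, as stated. Sample size: 3 × 8 = 24, as stated.

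**Interval outside the medication tables.** Length = SFU day − TOC day.
- Shortest: 28 − 15 = 13 days.
- Longest: 35 − 8 = 27 days.

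As a share of the time from first dose to SFU, (SFU − TOC) / (therapy days + SFU):
- Smallest: 13 / (14 + 28) = 13/42 = 31%.
- Largest: 27 / (2 + 35) = 27/37 = 73%.

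**Effect of one infant counted only through the mother.** 1/24 = 4.2 percentage points overall; 1/8 = 12.5 points in a cohort. An infant who also received the class is already counted once, so the mother's use then adds nothing.

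**Illustration of over-counting, on assumed rates.** Let p be the share of infants truly using a class, b the share breast-fed and q the share of those mothers using the class, with maternal and infant use independent. Then

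excess = (1 − p) × b × q.

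The assumed ranges are p 10–50%, b 50–80% and q 10–50%.
- Low: 0.50 × 0.50 × 0.10 = 2.5 points, or 24 × 0.025 = 0.6 infants.
- High: 0.90 × 0.80 × 0.50 = 36 points, or 24 × 0.36 = 8.6 infants.

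**Illustration of omission, on assumed rates.** Let 25% of infants use a class by TOC, and let a share s of the remainder first start it between TOC and SFU. Then

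missed = 0.75 × s.

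- s = 5%: 3.8 points, or 0.9 infants of 24. Chance of missing at least one infant: 1 − (1 − 0.0375)^24 = 60%.
- s = 20%: 15 points, or 3.6 infants of 24. Chance of missing at least one infant: 1 − (1 − 0.15)^24 = 98%.

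These two illustrations show how the error scales. They do not estimate what happened in this trial.

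**Cross-reference.** SAP 4.2.4 sends the reader to Section 3.3.3 for the definitions. Section 3.3.3 covers exposure and compliance; the definitions are in 3.3.2.

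**The case against.** The strongest reply has four parts.

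1. *The SAP does not say how maternal records will be displayed.* The table shells are not in the documents, so a separate maternal block there cannot be excluded. That is true, but the SAP text puts maternal drugs into summaries whose stated statistic is a count of patients, and unseen shells do not override it.

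2. *The TOC limit is a definition, not a miscount.* SAP 4.2.4 introduces the table as "Medications received concomitantly with study therapy, categorized by anatomical therapeutic chemical classification and generic name", and a drug started by TOC and continued afterwards is still counted. This stands in part. The window already runs 8 to 15 days beyond the last dose, however, so it is not confined to co-administration. No reason is given for stopping short of both the protocol's collection period and the adverse-event window.

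3. *Nothing is lost, because medication data are listed by patient for the ITT set.* It is fair that absence from a table is not loss of the data. The listing is only a partial safeguard: the SAP does not say that it marks maternal records or covers records after TOC.

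4. *The headline results do not depend on this table.* This stands in full. A reader might infer that the cure rate or the protocol deviations are distorted. Clinical outcome is assessed by the investigator and derived by SAP Table 6. Important deviations come from the deviation guidance document and CTMS (SAP 2.2). Drugs started after TOC also come too late to confound a cure rate read at TOC.

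A reader might also infer that transfusion use could be inflated by maternal transfusions. The protocol names transfusions among the treatments to be documented, but for the mother asks only for medications taken. Only under-counting is well supported for transfusions.

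**Conclusion.** The point holds as a defect in the definitions behind the descriptive medication tables. As written, they can attribute a mother's drug to her infant, in both the use tables and the prior-medication duration summary. They also leave an infant drug or transfusion first started after TOC outside every medication table, for an interval of 13 to 27 days.

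The per-infant increments of 4.2 and 12.5 points assume the planned 24 patients and cohorts of 8, and apply only to an infant not otherwise counted in that class.

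A reader might go further and conclude that the reported use is wrong in both directions. The documents do not show that. An over-count requires a mother on a class her infant did not receive; an omission requires a first start after TOC. No rates are given for either, so the net error in this trial cannot be computed. What is affected is interpretation of infant concomitant treatment, chiefly antibacterials and transfusions, and not the adverse-event summaries.

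**What to change.** - **SAP 4.2.4:** tabulate infant medications only, including the duration of prior medications, and show maternal medications in a separate, flagged table or listing.
- **SAP 3.3.2:** end the concomitant period at the SFU visit instead of TOC. Alternatively, keep the TOC limit and add a table of infant medications and transfusions from after TOC to SFU.
- **SAP 4.2.4:** correct the cross-reference for the definitions from Section 3.3.3 to Section 3.3.2.

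The cost is one subject flag in programming and one extra table. The protocol already requires the data, so no new collection is needed.

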4.2.5 Study therapy exposure and compliance

Duration of study therapy exposure in days for ceftaroline fosamil, optional ampicillin and optional aminoglycoside will be tabulated by age cohort and overall for the Safety Analysis Set and MITT population. In addition to standard summary statistics, quartiles for each patient and total treatment days for all patients will be shown.

Following protocol amendment 2 the dose of ceftaroline fosamil was changed from 4mg/kg to 6mg/kg. No summaries will be provided by the different ceftaroline fosamil doses, under the different versions of the protocol to which patients were enrolled.

Treatment compliance will be summarized as continuous data and categorically (<80%, 80-120%, >120% compliance) by age cohort and overall for the Safety Analysis Set and MITT population.

Ceftaroline fosamil exposure data, compliance data and administration details will be listed by age cohort and patient for the Safety Analysis Set.

4.2.6 Safety analysis

4.2.6.1 Analysis of adverse events, serious adverse events, and deaths

The number and percentage of patients with AEs occurring after the start of administration of the first dose of study therapy, or AEs that started prior to treatment and worsened on treatment, up to the SFU visit will be summarized, i.e. treatment emergent(TE) AEs. The following summaries will be presented for the Safety Analysis Set:

- Overall summary of TEAEs by category (overall and by age cohort)
- Incidence of TEAEs by system organ class (SOC) and preferred term
- Incidence of TEAEs by SOC, preferred term, and maximum intensity
- Incidence of TEAEs by SOC, preferred term, and relationship to ceftaroline
- Incidence of TEAEs of special interest by SOC and preferred term
- Incidence of non-serious TEAEs by SOC and preferred term
- Incidence of TEAEs with fatal outcome by SOC and preferred term
- Incidence of all deaths
- Incidence of Serious TEAEs by SOC and preferred term
- Incidence of TEAEs leading to discontinuation of investigational product by SOC and preferred term

All AEs occurring prior to the first intake of ceftaroline will be listed for the Safety Analysis Set.

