7.1.2. Ampicillin and Optional Aminoglycoside

Ampicillin (if mandated as per [Section 7.2.2](#)) is to be initiated at Baseline and to be administered for at least 48 hours (minimum duration of study therapy); after 48 hours, the duration of treatment with ampicillin is at the discretion of the investigator.

The use of an aminoglycoside is considered optional from Baseline through the entire study, ie, may be started and stopped at any time during the study at the discretion of the investigator.

Consult the product package insert, label, and local dosing guidelines for further information regarding dosage, administration, storage, maximum doses, contraindications, warnings, precautions, and AEs reported.

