The study design is described in the Study Diagram ([Figure 1](#)). Patient participation will require up to 49 days (up to 14 days of treatment plus up to 35 days of safety follow-up). The total duration of study therapy is 48 hours (minimum) to 14 days (maximum). Hospitalization is required during IV study therapy. Baseline assessments for study eligibility will occur within 36 hours before the first dose of study therapy.

Procedures will be performed according to the Study Plan in [Table 1](#). Safety assessments will be done throughout the study. Between Day 2 and Day 14, 2 blood samples will be collected for PK analysis. The efficacy of ceftaroline fosamil will be evaluated based on the clinical outcome (clinical cure, clinical failure or indeterminate) at end of therapy (EOT; within 24 hours after completion of last infusion) and test-of-cure (TOC; 8 to 15 days after the last dose of study therapy) assessments. The Safety Follow-up (SFU) assessments will occur 28 to 35 days after the last dose of study therapy. Adverse events (AEs) will be followed up in the study until SFU.

A patient who is prematurely discontinued from study therapy administration for any reason will have EOT assessments conducted and undergo subsequent safety assessments at TOC and SFU per protocol.

[figure not shown]
- If a patient is prematurely discontinued from study therapy due to an adverse event and the clinical signs and symptoms of sepsis have resolved completely or improved such that no further antibacterial therapy is necessary, the patient will be assessed as a clinical cure at EOT and reassessed at TOC.
- If a patient is prematurely discontinued from study therapy due to a study therapy-related AE and requires alternative non-study antibacterial for treatment for LOS, the patient will be assessed as a clinical failure (or indeterminate, if the patient discontinued before minimum treatment duration) at EOT and TOC.
- If a patient is prematurely discontinued from study therapy administration (at any time after the required minimum treatment duration of 48 hours) due to insufficient therapeutic effect, the patient will be assessed as a clinical failure on the day of discontinuation (ie, EOT) and at all subsequent evaluation time points.

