2.1.2 Safety Analysis Set

The Safety Analysis Set will be a subset of the ITT Analysis Set and will include all patients who received any amount of ceftaroline fosamil.

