3. PRIMARY AND SECONDARY VARIABLES

For the calculation or derivations of the variables in this section, baseline will be defined as the last non-missing value before the start of study therapy. Change from baseline variables will be calculated for clinical laboratory tests and vital signs parameters as the post-treatment value minus the value at baseline. The visit windows for EOT, TOC, and SFU are defined in [Table 2](#) for efficacy analyses.

Study days are to be calculated starting from the onset of the first dose of study therapy, in 24-hour increments. If a date is prior to the first study therapy dose date (eg, date of LOS diagnosis, prior medication start date) then the study day will be calculated as (past date – first

study therapy dose date); if the assessment date is on or after the first study therapy dose date then the study day will be calculated as (assessment date – first study therapy dose date + 1). Durations in days will be calculated as (end date – start date +1).

Table 2 Visit Windows for EOT, TOC, and SFU

Visit	Protocol-defined Window
End of IV therapy (EOT)	Within 24 hours of completion of the last infusion of study drug
Test of cure (TOC)	8 to 15 days after the last dose of study drug
Safety follow-up (SFU)	28 to 35 days after the last dose of study drug

NB. Since there is no per protocol population defined for this study, scheduled visits will be used for MITT analyses and derived analysis windows will not be evaluated.

For analyses purposes, nominal visit data was used.

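### The treatment-emergent window starts at the first dose of any study therapy rather than of ceftaroline, and no planned summary separates AE onset during treatment from onset in follow-up

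*SAP*

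**What the plan says.** **Start of the window.** SAP 4.2.6.1 counts "AEs occurring after the start of administration of the first dose of study therapy", together with earlier AEs that worsened on treatment. SAP 3.1.1.1 uses the same start for AEs and for treatment-emergent SAEs. SAP 1.2 defines study therapy as ampicillin plus an optional aminoglycoside with ceftaroline added. Protocol 7 names ceftaroline fosamil alone as the investigational product. Protocol 7.1.2 says that ampicillin, where mandated, "is to be initiated at Baseline and to be administered for at least 48 hours", and lets the aminoglycoside start and stop at any time.

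**What is tied to ceftaroline.** The primary objective (SAP 1.1.1) is the safety of ceftaroline. The Safety Analysis Set is "all patients who received any amount of ceftaroline fosamil". SAP 4.2.6.1 tabulates relationship to ceftaroline, and it closes with: "All AEs occurring prior to the first intake of ceftaroline will be listed for the Safety Analysis Set".

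**End of the window.** Events "up to the SFU visit will be summarized, i.e. treatment emergent(TE) AEs". SAP 1.2 anchors SFU to the combination: "The Safety Follow-up (SFU) assessments will occur 28 to 35 days after the last dose of study therapy". SAP Table 2 uses a different term: "28 to 35 days after the last dose of study drug". Protocol 6.1.4 gives two ends for AE collection: at least 28 days after the last investigational product, and the SFU visit.

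**Summaries.** SAP 4.2.6.1 lists ten. None splits onset by treatment period, and no AE rate per patient-day is planned, although SAP 4.2.5 tabulates treatment days.

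**The concern.** There are two separate problems.

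The first is a contradiction within SAP 4.2.6.1. The tables start at one drug and the pre-treatment listing ends at another. An AE between the first ampicillin or aminoglycoside dose and the first ceftaroline infusion meets both definitions, so it enters the primary safety tables for a drug the infant had not yet received.

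The second is that a short course and a long follow-up are reported as one number. The trial has 24 infants, one arm and no comparator, and Protocol 6.2.1 counts worsening of the underlying disease as an AE. Onset relative to exposure is then one of the few objective aids to attribution, and the planned tables do not show it. A reader of the pooled incidence cannot tell an event during infusions from one four weeks later.

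**Working it through.** **Inputs.** Therapy lasts t = 2 to 14 days and SFU falls f = 28 to 35 days after the last dose (SAP 1.2). Steps 1 and 2 assume that ceftaroline runs for the whole of study therapy and that every infant reaches SFU.

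**1. The plan's own figure.** SAP 1.2 gives maximum participation as "up to 14 days of treatment plus up to 35 days of safety follow-up": 14 + 35 = 49 days, which reproduces the stated 49. The shortest window is 2 + 28 = 30 days.

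**2. Share of the window after treatment, f / (t + f).**

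| Therapy (days) | SFU day 28 | SFU day 35 |
|---|---|---|
| 2 | 28/30 = 93.3% | 35/37 = 94.6% |
| 7 | 28/35 = 80.0% | 35/42 = 83.3% |
| 14 | 28/42 = 66.7% | 35/49 = 71.4% |

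More than half of the window is after treatment in every permitted combination.

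**3. Does re-anchoring change this?** Let ceftaroline run c days within T days of study therapy. As written, the off-ceftaroline share is (T + f − c) / (T + f). Anchored to ceftaroline at both ends, it is f / (c + f). The gaps below are assumptions, because the documents give none.

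- c = T: no change.
- 36-hour lead-in, c = 12.5 and T = 14: 29.5/42 = 70.2% becomes 28/40.5 = 69.1% (SFU day 28), and 36.5/49 = 74.5% becomes 35/47.5 = 73.7% (day 35).
- Extreme case, c = 2 and T = 14: 40/42 = 95.2% becomes 28/30 = 93.3%, and 47/49 = 95.9% becomes 35/37 = 94.6%.

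The off-drug share comes from the length of follow-up. The anchors move it by about two percentage points at most in these cases.

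**4. Does time share carry over to incidence?** The tables count patients with at least one event. Under an assumed constant hazard h per day, the share of affected patients whose first AE falls on treatment is [1 − exp(−ht)] / [1 − exp(−h(t + f))].

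- t = 14, f = 28: 13.1%/34.3% = 38.1% at h = 0.01, and 75.3%/98.5% = 76.5% at h = 0.10.
- t = 2, f = 35: 2.0%/30.9% = 6.4% at h = 0.01, and 18.1%/97.5% = 18.6% at h = 0.10.
- t = 14, f = 28, with a hazard of 0.03 on treatment and 0.01 afterwards: [1 − exp(−0.42)] / [1 − exp(−0.70)] = 34.3%/50.3% = 68.1%.

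The answer depends on hazards that the documents do not give.

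**The case against.** **The start gap may be almost nothing.** Protocol 4.2.1.1 puts ceftaroline and ampicillin together on Study Day 1. Protocol 4.1 places Baseline before the first dose of study therapy, and the SAP study plan shows no study therapy in the Baseline column. This stands as a limit on size. It does not remove the double classification, which nothing in the text resolves.

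**Attribution and timing are partly covered.** SAP 4.2.6.1 plans tables by relationship to ceftaroline and of discontinuation of investigational product. Laboratory summaries are by visit, ceftaroline administration is listed per patient, and 24 infants can be read one by one. This also stands in part. However, relationship is open-label judgement, and its reference differs: SAP 3.1.1.1 assesses it against study therapy, Protocol 6.1.5 against the investigational product. A listing also leaves the split to be made after the data are seen.

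**Re-anchoring has a side effect.** SAP 3 and Protocol 8.5.2 set the safety baseline at the start of study therapy, so moving only the AE start would misalign the two. The point is sound, and the fix must address it.

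**A post-ceftaroline column is not drug-free.** Protocol 1.3 warns of anaemia during or after treatment, and any 24-hour cut-off is a convention. Both are correct, which is why the planned total should stay.

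**Conclusion.** The concern holds as an inconsistent start anchor plus a missing onset split. The anchor defect is certain in the text; its practical size is unknown and probably small. The off-treatment share of 67% to 95% follows from the SAP's own durations, given the assumptions in the working. Pooled single-arm incidence over that window cannot by itself separate on-drug events from later background events.

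A reader might infer three stronger things that the documents do not support.

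- *That AE incidence mainly reflects the natural course of sick infants.* No background AE rate is given, and under the assumed hazards shown the on-treatment share of first AEs runs from 6% to 76%.
- *That the anchors cause the large off-drug share.* Follow-up does; anchoring both ends to ceftaroline still leaves 67% to 95%.
- *That follow-up dilutes an on-drug signal.* The denominator is a fixed number of patients, so later time can add affected patients but cannot remove an on-drug case. It obscures timing and does not lower incidence.

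**What to change.** 1. In SAP 3.1.1.1 (AE and SAE definitions) and 4.2.6.1, start the treatment-emergent window at the first ceftaroline fosamil infusion. Use AE onset time where available, and state one rule for date-only onsets. Put earlier events in the pre-ceftaroline listing only. If the drugs start on the same date and no AE time exists, the rule decides the class and cannot recover the true order; say so.
2. State how this start aligns with the safety baseline in SAP 3.
3. Use one term for the last dose that anchors SFU in SAP 1.2, SAP Table 2 and Protocol 6.1.4.
4. Keep the planned total through SFU. Add on-ceftaroline and post-ceftaroline onset columns to the TEAE, serious TEAE and relationship tables, overall and by cohort. Prespecify the cut-off as a convention, for example 24 hours after the last ceftaroline infusion, and note that the later column may contain delayed drug effects.

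The cost is wording, one derived flag and a boundary-day rule. Infusion dates and times are already recorded (Protocol 7.5), so no new exposure data are needed. The downside is a few extra columns with small counts, since each cohort has 8 infants.
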